4.4.7 Time to QOL deterioration

The analysis will be done if we have the questionnaire at baseline and at least one follow-up for the majority of patients.

4.4.7.1 Definition

It is defined as the time between the date of inclusion and the date of deterioration of the Spitzer QoL Index by 2 points from the score at inclusion. Patients alive or deceased without deterioration will be censored at the date of last QoL assessment or the date of death.

4.4.7.2 Evaluation

The time scale considered will be the month.

The time to deterioration of quality of life will be plotted using the Kaplan Meier estimator, and the 6-, 9-, 12-, and 18-month rates will be calculated along with their 95% confidence intervals.

4.5 Safety

Population : ITTm

Safety will be evaluated by:

- Duration of treatment, doses received, dose reductions, and deferrals;
- Toxicities described according to NCI-CTC version 4.0 criteria;
- Number and description of SAEs

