## 8. PATIENT MONITORING

### 8.1 during treatment :

- Clinical examination: weight, height, BP, collection of toxicities and clinical tumor assessment

- Cycle 1 and 2: at D1, D7 and D14
- Cycles 3 and following: at D1 of each cycle
- At the end of treatment visit

The ECOG is completed on Day 1 of each cycle (cycle 1 and following) and at the end-of-treatment visit.

- Bioassay:

At each cycle: at D1 and D14; (for cycle 1, the biological test at D1 can be the inclusion test, if it is less than 14 days old).

The assessment at Day 1: CBC-platelets, natraemia, kalemia, calcemia, magnesemia, phosphoremia, uricemia, creatininemia, creatinine clearance, albuminemia, ASAT, ALAT, PAL, total and conjugated bilirubinemia, GGT, TP, TSH, lipase, INR for patients treated with AVK.

Assessment at D14: CBC/blood platelets, creatinine clearance, natraemia, kalemia, creatinine, ASAT, ALAT, PAL, total and conjugated bilirubin, GGT, INR for patients treated with AVK.

- At the end-of-treatment visit: CBC/blood platelet count, natraemia, kalemia, creatinine, creatinine clearance, AST, ALT, PAL, total and conjugated bilirubin, GGT

A coagulation test should be performed at D1 and D14 of each cycle, if patients are treated with anticoagulant. If the values are outside the therapeutic range, the dose of anticoagulant should be modified and a coagulation test should be performed every week until stabilization.

- Other follow-up:

During treatment, an ECG will be performed if deemed useful by the investigator.

Every 4 weeks, until progression, CEA measurement will be performed as well as quality of life and geriatric parameters assessment.

Every 8 weeks, until progression, a thoraco-abdomino-pelvic scan will be performed to evaluate the tumor response.

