## **8.2 After treatment :**

- If treatment is stopped for progression: the patient will be followed up approximately every 8 weeks to collect survival data and subsequent anti-cancer treatments.

- if the treatment is stopped for another reason: the patient will be followed every 8 weeks with a thoraco-abdomino-pelvic scanner, until progression. Then he will be followed approximately every 8 weeks to collect survival data and subsequent anti-cancer treatments.

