## **11.4 Statistical analysis**

### **Populations of analysis**

All analyses will be done on an intention-to-treat basis on all included patients who have taken at least one treatment tablet.

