2.1.2 Modified Intent-to-treat population (ITT_m)

The modified intention-to-treat population is defined as all patients included in the study who received at least one regorafenib tablet and had at least one imaging assessment under protocol treatment.

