2.1.3 Safety population (PT)

The safety population is defined as all patients included in the study who received at least one regorafenib tablet.

3 Statistical Generalities

Analyses will be done by CRGA.

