3.5 Statistics

The confidence intervals provided will be two-sided 95% confidence intervals except for the primary criterion where the calculated confidence interval will be a one-sided 95% confidence interval.

Quantitative data will be described using the following descriptive statistics: number, mean, standard deviation, median, first and third quartile, and minimum and maximum. These statistics will be considered the usual statistics for the analysis of quantitative variables. Quantitative variables may be categorized using their median or a cut-off known from the medical literature.

Categorical variables will be summarized using the following descriptive statistics: the number, frequencies and percentages for each level of the variable. These statistics will be considered the usual statistics for the analysis of categorical variables.

When necessary, the 95% confidence intervals for the proportions can be calculated from the exact binomial distribution.

Survival data will be estimated and plotted using the Kaplan Meier method (Kaplan and Meier., 1958). They will be described by the median and rates calculated at different time points with their two-sided 95% confidence intervals. Confidence intervals for the rates will be constructed from the Greenwood variance calculated using the log-log transformation.

Median follow-up time will be estimated using the inverse Kaplan-Meier method (Shemper, 1996).

As an exploratory measure, for uni and multivariate analyses, the hazard ratios will be estimated using a Cox model (Cox, 1984). The hypothesis of proportionality of the rates will be tested using the graphical representation and the test based on Schönfeld's residuals (Grambsch, 1994); the linearity of the effect of the continuous variables on the risk will be evaluated from the graphical representation of the martingale residuals. Confidence intervals for the coefficient estimates of the Cox models will be calculated using the Wald method.

4 Analyses statistiques

	ITT Population	ITTm Population	Population de tolérance
Baseline description			
Eligibility	X		
Demographics	X		
Clinical characteristics	X		
Biological characteristics	X		
Disease characteristics	X		
Main criterion			
Tumoral control	X		
Critères secondaires			
Follow-up time	X		
OS, PFS	X		
Tumoral control (Centralised review)	X		
Objective response	X		
Time to therapeutic failure	X		
Time to autonomy deterioration	X		
Time to QOL deterioration	X		
Safety			
Treatment			X

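### SAP 4.5 assigns the safety analysis to the ITTm set, in conflict with the SAP's own population table and Protocol 11.4

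*SAP*

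**What the plan says.** The SAP defines two populations that matter here:

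- **Safety population (SAP 2.1.3):** "The safety population is defined as all patients included in the study who received at least one regorafenib tablet".
- **ITTm (SAP 2.1.2):** included patients who "received at least one regorafenib tablet and had at least one imaging assessment under protocol treatment".

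Three places assign the safety analyses to a population:

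- **SAP 4.5 Safety** is headed "Population : ITTm", directly above the line that begins "Safety will be evaluated by". The header covers treatment duration, doses, dose changes, reasons for stopping, graded toxicities and SAEs. Subsections 4.5.1 to 4.5.3 name no other population.
- **The table in SAP section 4** (printed after 3.5) marks Treatment and Toxicities in the column "Population de tolérance". Its ITTm column has no mark in any row.
- **Protocol 11.4, Populations of analysis:** "All analyses will be done on an intention-to-treat basis on all included patients who have taken at least one treatment tablet".

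On scan timing, Protocol 8.1 states "Every 8 weeks, until progression, a thoraco-abdomino-pelvic scan will be performed to evaluate the tumor response". For patients who stop for a reason other than progression, Protocol 8.2 adds that "the patient will be followed every 8 weeks with a thoraco-abdomino-pelvic scanner, until progression".

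**The concern.** The SAP gives two different denominators for the same tables, and nothing in it says whether a section header or the section 4 table takes precedence. If the choice is left open, it could be made after the data have been seen.

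ITTm is a poor set for safety because membership depends on something that happens after treatment starts: the patient must stay on study long enough to be scanned. Patients who die early, or who stop for toxicity before a scan, are the ones a tolerance analysis most needs to keep. Under the header they would be missing from treatment duration, from dose modifications, from the count of permanent discontinuations with reasons (4.5.1.3) and from the graded toxicities (4.5.2).

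Tolerance of regorafenib in patients aged 70 or more is a stated secondary objective (Protocol 2.2, SAP 1.1.2). A rate calculated on ITTm would not describe all treated patients.

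**Working it through.** **1. The sets compared**

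| Source | Set for safety | One tablet | On-treatment scan |
|---|---|---|---|
| SAP 4.5 header | ITTm | required | required |
| SAP section 4 table (Treatment, Toxicities) | Safety population | required | not required |
| Protocol 11.4 (all analyses) | All included and treated | required | not required |

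ITTm is therefore the safety population minus the treated patients with no imaging assessment under protocol treatment. The last two rows describe the same set; only the header differs.

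**2. Does the table settle it?** Not by any stated rule. The SAP text also departs from the table for the primary endpoint: sections 4.3 and 4.3.2 use ITTm, while the table marks ITT. A programmer cannot assume that the table overrides the section text.

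**3. Could the excluded group be non-empty?** Scheduled scans start at 8 weeks, day 56. Protocol 1.2 quotes a median treatment duration of 7.1 weeks in patients over 65 in the earlier phase III trial: 7.1 × 7 = 49.7 days. Some exclusions are plausible, but this does not mean that half would be excluded:

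- The last tablet of cycle 2 falls on day 28 + 21 = 49, so a patient who completes two cycles may still be scanned at week 8.
- A patient scanned earlier stays in; SAP 4.3.1 foresees imaging before 2 months.
- The SAP does not say whether a scan after the last tablet counts as under protocol treatment. The excluded share depends on that reading.

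**4. Effect on a reported rate.** Let p be the true rate among all treated patients, e the share excluded and q the event rate among those excluded. Then

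reported rate = (p − e·q) / (1 − e).

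The rate is understated if q > p, overstated if q < p and unchanged if q = p.

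For p, Protocol 1.2 gives regorafenib-related grade 3 or higher rates of 66% (over 75 years) and 57% (65 to 74 years). The documents give neither e nor q; the values below are assumptions.

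| p | q | e = 10% | e = 15% | e = 20% |
|---|---|---|---|---|
| 66% | 100% | 62.2% | 60.0% | 57.5% |
| 66% | 80% | 64.4% | 63.5% | 62.5% |
| 66% | 66% | 66.0% | 66.0% | 66.0% |
| 66% | 40% | 68.9% | 70.6% | 72.5% |
| 57% | 100% | 52.2% | 49.4% | 46.3% |
| 57% | 80% | 54.4% | 52.9% | 51.3% |
| 57% | 57% | 57.0% | 57.0% | 57.0% |
| 57% | 40% | 58.9% | 60.0% | 61.3% |

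Worked cell: (0.66 − 0.15 × 1.0) / 0.85 = 0.51 / 0.85 = 60.0%.

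**5. The same in whole patients.** Assume 42 treated, 28 of them with an event (66.7%), and 4 with no on-treatment scan. The reported rate is (28 − 4)/38 = 63.2% if all four had an event and 28/38 = 73.7% if none did.

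**6. Design figures.** The plan's 42 patients with success at 16 or more reproduce under the exact binomial: one-sided alpha 0.0416 at 25% and power 0.9057 at 47%. Changing the safety population alters neither figure.

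**The case against.** The strongest reply is that this is an evident slip in one header. The section 4 table and Protocol 11.4 agree on the one-tablet set, and the table uses the safety population for nothing except these rows. The primary endpoint is a weaker parallel, because there the table (ITT), SAP 4.3 (ITTm) and Protocol 11.4 (one tablet) give three different sets. The output at stake is descriptive, with no safety test or threshold. The independent committee's review of safety data (Protocol 13.2) does not depend on the header, and serious early cases may still appear in the pharmacovigilance summary (SAP 4.5.3). With 42 patients, a 66% rate also carries a 95% interval of about ±14 points (1.96 × √(0.66 × 0.34 / 42) = 0.143).

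Much of this is fair. A slip is the most natural reading. SAP 2.1.3 only defines a population, so the direct conflicts of assignment are with the table and Protocol 11.4. The table has no SAE row, so for SAEs the support comes from Protocol 11.4 alone. The percentages above illustrate a mechanism and are not evidence of its size.

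The contradiction remains all the same. A slip in the operative section still directs the programmer to the wrong denominator. The SAE summary does not supply exposure, dose changes, reasons for stopping or non-serious graded toxicities. Sampling error is no defence for selecting patients on a post-baseline event.

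**Conclusion.** The concern holds and must be fixed. The header of SAP 4.5 contradicts the section 4 table and Protocol 11.4, and leaves the population defined in 2.1.3 unused in the section it was written for. Confidence in the contradiction is high.

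The size and direction of the effect are not known. Over the assumed ranges (10% to 20% excluded, event rate among them 40% to 100%), the reported grade 3 or higher rate moves from about 11 points too low (57% to 46.3%) to 6.5 points too high (66% to 72.5%), and it does not move if the excluded patients have the average rate. If every treated patient has an on-treatment scan, the two sets coincide and nothing changes. The primary endpoint, the sample size and the decision rule are not affected by this point.

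**What to change.** Before the database is frozen, change the population named in the header of SAP 4.5 from ITTm to the safety population of section 2.1.3, and apply it to 4.5.1, 4.5.2 and 4.5.3. This agrees with the section 4 table for treatment and toxicities and with Protocol 11.4 throughout. Adding an SAE row to the table would close the remaining gap.

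The cost is a change to one term in the SAP. No new data are needed, and SAP 1.6 allows modifications up to database freeze. Once safety no longer uses ITTm, the unclear meaning of imaging under protocol treatment ceases to matter for these tables.

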4.5.1 Regorafnib

4.5.1.1 Treatment duration

Treatment duration will be described by:

- The number of cycles per patient;
- The duration of treatment (converted into months) will be calculated by the formula
$$\text{Date last tablet taken} - \text{date first tablet taken} + 1d$$
- The therapeutic breaks and the days without taking tablets during this period will not be subtracted from this duration.

It will be described according to the usual descriptive statistics.

4.5.1.2 Doses

Compliance will be calculated according to the formula:

$$(\text{Cumulative dose received (in mg)} / \text{theoretical protocol dose (in mg)}) \times 100$$

The protocol treatment dose is 4 tablets of 40 mg per day, i.e. 160 mg per day (21 days of treatment and 7 days without treatment, i.e. cycles of 28 days).

Compliance will be described according to the usual descriptive statistics.

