## 7. TREATMENT

Regorafenib is not provided as it is in its indication.

The initial dose will be 160 mg (4 tablets) taken orally once daily for 21 days, followed by 7 days without treatment.

They should be taken at a fixed time and in one go at the end of a light meal in a large glass of water.

Forgotten or vomited tablets should not be taken again.

Dose modifications will be made according to the protocol in 40 mg steps. The minimum recommended dose is 80 mg.

Reasons for dose reduction or discontinuation of treatment will be collected in the observation booklet.

Compliance with the treatment will be evaluated for each cycle by the investigator, using the compliance booklet given to the patient at the beginning of the treatment and reported at each consultation. This compliance will be reported in the observation booklet.

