### 7.2 Dose adjustment

Toxicities will be evaluated by questioning and clinical examination at D1, D7, and D14 of the 1st cycle and of the 2e cycle then at D1 of each following cycle. They will be evaluated by biology at D14 and D28 of each cycle. They will be graded according to the NCI-CTC AE version 4.0 criteria (Appendix 7).

The decision to reduce the dose is based on toxicity throughout the cycle.

The doses will be adapted according to the RCP (see table below).

Discontinuation of treatment and/or reduction in dosage may be necessary depending on tolerance. Dosage changes should be made in 40 mg (one tablet) increments. The minimum recommended daily dose is 80 mg. The dose may be increased if there is complete recovery of the side effect after dose reduction. The maximum daily dose is 160 mg.

A) Dosage modifications and recommended actions for hand-foot syndrome (MPS/palmoplantar erythrodysesthesia):

Grade of skin toxicity	Occurrence	Dosage changes and recommended actions
Grade 1	All cases	Maintain dosage and institute symptomatic treatment immediately.
Grade 2	1 re occurred	Reduce the dose by 40 mg (one tablet) and start symptomatic treatment immediately.
	No improvement within 7 days or 2 e occurred	Interrupt treatment until toxicity disappears or decreases to a grade $\leq$ 1. When treatment is resumed, reduce the dose by 40 mg (one tablet).
	3 e occurred	Immediately initiate symptomatic treatment. Interrupt treatment until toxicity has resolved or decreased to a grade $\leq$ 1. When treatment is resumed, reduce the dose by 40 mg (one tablet) if it had been increased after previous episodes.
	4 e occurred	Stop the treatment permanently.
Grade 3	1 re occurred	Immediately institute symptomatic treatment. Interrupt treatment for a minimum of 7 days until toxicity disappears or decreases to a grade $\leq$ 1. When treatment is resumed, reduce the dose by 40 mg (one tablet).
	2 e occurred	Immediately institute symptomatic treatment. Interrupt treatment for a minimum of 7 days until toxicity disappears or decreases to a grade $\leq$ 1. When treatment is resumed, reduce the dose by 40 mg (one tablet).
	3 e occurred	Stop the treatment permanently.

Treatment should be permanently discontinued in case of intolerance to the 80 mg daily dose.

B) Dosage modifications and recommended actions for drug-related liver function abnormalities

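### SAP 4.5.1.2 labels as compliance a ratio to a fixed 160 mg per day, which is in substance the protocol's relative dose intensity and not adherence to the prescribed tablets

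*SAP*

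**What the plan says.** **The SAP.** Section 4.5.1.2 opens with "Compliance will be calculated according to the formula" and then divides the cumulative dose received (mg) by the theoretical protocol dose (mg), times 100. The reference dose follows: "The protocol treatment dose is 4 tablets of 40 mg per day, i.e. 160 mg per day", for 21 days of each 28-day cycle. No adjustment for ordered reductions or holds is given. On reporting: "Compliance will be described according to the usual descriptive statistics".

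**The protocol on dosing.** Section 7: "The initial dose will be 160 mg (4 tablets) taken orally once daily for 21 days, followed by 7 days without treatment", and "Dose modifications will be made according to the protocol in 40 mg steps". Section 7.2: "The minimum recommended daily dose is 80 mg". Its toxicity tables also require interruptions, and section 7.1 ends treatment if more than two 40 mg reductions would be needed.

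**The protocol on compliance.** Section 7: "Compliance with the treatment will be evaluated for each cycle by the investigator, using the compliance booklet given to the patient". The result is entered in the observation booklet.

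**The protocol on dose intensity.** Section 11.1 (secondary criteria) defines relative dose intensity as the dose intensity received over a theoretical 3360 mg per cycle. It is to be calculated for the first two cycles and for the whole treatment period. SAP 1.1.2 lists dose intensity and its correlation with disease control among the objectives, but the SAP gives no formula under that name.

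**The concern.** The protocol treats two things separately: how much drug a patient received relative to the full schedule (dose intensity), and whether the patient took what was prescribed (compliance). The SAP formula measures the first and gives it the name of the second.

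A patient moved to 120 or 80 mg under Protocol 7.2 is following the protocol. With a fixed 160 mg reference, each ordered reduction or hold lowers that patient's compliance figure just as forgotten tablets would. The more toxicity there is, the lower compliance looks, even if every prescribed tablet is taken.

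The trial sets out to describe a self-administered oral drug in patients aged 70 or over, with tolerance among its secondary objectives. Protocol 1.2 cites regorafenib-related grade 3 or higher events in 57% of patients aged 65 to 74 and 66% of those over 75 in the phase III trial, so dose changes can be expected to be common. At stake is how the exposure table reads: a low median labelled compliance invites the reading that older patients do not take their tablets.

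**Working it through.** **Inputs.** Starting dose 160 mg for 21 of 28 days, 40 mg steps, minimum 80 mg (Protocol 7 and 7.2). Formula and fixed reference (SAP 4.5.1.2). Tablets of 40 mg.

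**The plan's own figure.** 160 mg × 21 days = 3360 mg per cycle, which reproduces the theoretical dose intensity in Protocol 11.1. The SAP's compliance denominator and the protocol's dose-intensity reference are the same quantity.

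**One full cycle, every prescribed tablet taken**

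| Prescribed daily dose | Dose taken | SAP formula | Taken / prescribed |
|---|---|---|---|
| 160 mg | 3360 mg | 3360/3360 = 100% | 100% |
| 120 mg | 2520 mg | 2520/3360 = 75% | 100% |
| 80 mg | 1680 mg | 1680/3360 = 50% | 100% |

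**Two different patients, one score.** Three cycles, reference 3 × 3360 = 10080 mg, or 252 tablets.

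- Patient A is prescribed 160, 120 and 80 mg in successive cycles, that is 84 + 63 + 42 = 189 tablets, and takes all of them: 7560/10080 = 75%.
- Patient B is prescribed 160 mg throughout, 252 tablets, and misses a quarter (63), so takes 189: again 7560/10080 = 75%.
- Tablets taken over tablets prescribed separates them: A 189/189 = 100%, B 189/252 = 75%.

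**Cumulative values from reductions alone, every prescribed tablet taken**

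- Cycle 1 at 160 mg, then 80 mg throughout. Over k cycles the score is 50% + 50%/k: 75.0% (k = 2), 66.7% (3), 62.5% (4), 58.3% (6), 54.2% (12).
- 160, then 120, then 80 mg onward: 87.5% (2 cycles), 75.0% (3), 68.8% (4), 62.5% (6).

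Because treatment starts at 160 mg, the cumulative value approaches 50% but does not reach it through reductions alone.

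**With interruptions (assumed example).** Seven days at 160 mg and a hold for the rest of cycle 1, then seven days at 120 mg and a hold for the rest of cycle 2: (1120 + 840)/6720 = 29.2%, with every prescribed tablet taken. This counts whole cycles in the denominator. The SAP does not say whether to use cycles or elapsed time.

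**The case against.** The strongest reply is that this is a labelling matter in a descriptive table. The section is headed Doses, a fixed 160 mg reference is the protocol's own choice for dose intensity, and adherence is not an endpoint in either document. Tolerance is judged by graded toxicities. SAP 4.5.1.3 also tabulates patients with deferrals, dose changes and permanent stops, with reasons, so a reader can see at cohort level how often doses were changed on order. All of this stands and limits the importance of the point. It does not remove it: counts of patients with at least one change cannot divide one patient's 75% into ordered reduction and missed tablets, above all when both occurred.

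Three stronger readings are tempting, and the documents support none of them.

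- A reader might infer that adherent patients will be classed as non-compliant. The SAP sets no cut-off and classifies nobody; it summarises a percentage.
- A reader might infer that 50% is the level to which reductions bring a patient's reported figure. It is the value of a single full cycle at 80 mg. Over a course that starts at 160 mg, reductions alone stay above it, while holds can take the value below it.
- A reader might take the median of 78.6% of planned dose in patients over 65 (Protocol 1.2) as a forecast of about 21% non-compliance here. That figure comes from another study, and the protocol does not define its denominator.

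Nor do the documents show that the compliance booklet is ignored. SAP 4.5.1.2 does not name the source of the dose received, which may well be the booklet. The fault lies in the denominator and the label.

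**Conclusion.** The point holds as a mislabelled exposure measure. Followed as written, SAP 4.5.1.2 reports relative dose intensity under the name of compliance, and the SAP contains no measure of tablets taken against tablets prescribed. Fully adherent patients on ordered reductions are summarised below 100%: 75% for a full cycle at 120 mg, 50% for a full cycle at 80 mg, and 75% over cycles at 160, 120 and 80 mg.

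These figures assume full 21-day dosing at each level and a denominator counted in whole cycles. How far the cohort median would shift depends on how often doses are reduced or held in this trial, which the documents cannot tell us. The primary endpoint, the decision rule and the survival endpoints do not use this ratio. It is worth correcting because the reported number would mislead and the repair is cheap.

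**What to change.** In SAP 4.5.1.2:

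1. Rename the existing ratio relative dose intensity and compute it as in Protocol 11.1: reference 3360 mg per cycle, over the first two cycles and over the entire treatment period. This also supplies the measure that the dose-intensity objective in SAP 1.1.2 needs. State the time unit. The duration in SAP 4.5.1.1 ends at the last tablet and so omits the final rest week; used directly, one full-dose cycle would give 3360/(21/28) = 4480 mg per cycle, or 133% of the reference. Counting duration in 28-day cycles avoids this.
2. Define compliance separately as tablets taken over tablets prescribed after ordered reductions and holds, per cycle and overall, from the booklet data entered in the observation booklet.

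**Cost.** SAP wording and one derived variable; SAP 1.6 allows such changes before the database is frozen. The new denominator needs the prescribed dose and the hold dates, since Protocol 7.2 provides for changes within a cycle. Protocol section 7 confirms only that compliance and the reasons for reduction or discontinuation are recorded. If prescribed doses and hold dates were not captured, report the investigator's per-cycle compliance assessment instead. No dosing rule is affected.
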